9.1.12. Reporting and follow-up of Adverse Events

9.1.12.1. Recording of AEs

All AEs, whether observed by the Investigator or designee or volunteered by or elicited from the subject, occurring after consent signature should be recorded individually in the CRF with the following information: the specific event or condition, the dates and times (using the 24 hour clock, where midnight is 00:00 and noon is 12:00) of occurrence, duration, severity, relationship to study medication, specific countermeasures, outcome, and whether considered non-serious or serious, drug-related or not. AEs will

be recorded from the time a subject has signed the ICF and throughout the study, including the follow up period. The solicited AEs should be reported by the investigator from the day of injection up to 14 days after each injection. The investigator should record all AEs for the whole period of the study.

An SAE must fulfill the requirements listed in the Section 9.1.3.

Outcome to Date of an AE are classified according to definitions described in section 9.1.9.

AEs will be coded by Data Management using the Medical Dictionary for Regulatory Activities (MedDRA) AE dictionary.

9.1.12.2. Recording of Adverse Events of special Interest (AESI)

A noteworthy event for the particular product or class of products that a sponsor may wish to monitor carefully. It could be serious or non-serious, and could include events that might be potential precursors or prodromes for more serious medical conditions in susceptible individuals.

In this study, the AESI for COVID-19 vaccine will be defined as:

[figure not shown]
- Acute respiratory distress syndrome (ARDS)
- Pneumonitis
- Acute cardiac injury
- Arrhythmia
- Septic shock-like syndrome
- Acute kidney injury
- Vasculitis
- Autoimmune disease (AID)
- Meningitis
- Atypical measles
- Anosmia
- Dysgeusia

The investigator should report all AESIs for the whole period of the study.

9.1.12.3. Reporting of Serious (Expected or Unexpected) AEs

[figure not shown]
If the Investigator identifies a SAE or a SUSAR, it should be reported by the Principal Investigator to the sponsor without delay. The investigator should report all SAEs for the whole period of the study.

To proceed with notifying the sponsor of a serious adverse event, the investigator completes an initial notification form and immediately faxed or emailed it to SGS Medical Affairs.

Any fatal or life-threatening event should be reported immediately by phone or fax to the Sponsor. These preliminary reports will be followed within 24 hours by more detailed descriptions that will include a completed SAE form, as described below.

If the investigator is not capable of declaring the serious adverse events by the means listed above, they contact Institut Pasteur exclusively on the following number or email inbox:

For regulatory purposes, initial SAE reports should be submitted to the Sponsor immediately and should include:

- a suspected investigational medicinal product
- an identifiable subject (e.g., study subject code number)
- an adverse event with a seriousness and the Investigator's assessment of the relationship to study drug
- an identifiable reporting source (investigator contact details)

Once faxed or emailed, the printed SAE form and accompanying documentation should be placed in the SAE section of the Investigator's site file.

The sponsor responsibility is to assess the relationship with the study vaccine and the expectedness of the reported serious adverse event.

Since healthy volunteers are considered in this study, the sponsor should report immediately:

- Any deaths, life threatening event,
- SAE and SUSARs including event of medical importance
- Serious safety-related protocol deviations

to Competent Authorities, Ethics committees, Eudravigilance registry, and inform the investigators of all study site.

The clock starts at the time a sponsor representative is formally informed and confirmed the receipt of the report. The report to Competent Authorities, Ethics committees Eudravigilance registry (EVCTM) should be done, without delay, as soon as the following data have been ascertained:

- a suspected relationship with the investigational medicinal product
- an identifiable subject (e.g., study subject code number)
- an adverse event with a seriousness and the Investigator's assessment of the relationship to study vaccine
- an identifiable reporting source (investigator contact details).

In all cases, all SUSAR, relevant complementary information should be collected and notified within 8 extra-days:

- From the first report for deaths and life-threatening event,
- From the end of the allowed delay set for other SUSAR and event of medical importance.

Expedited reporting to CAs, ECs and investigators of each site will be managed by SGS Medical Affairs according to the SOP “Processing and Reporting of Individual Serious Adverse Events of Interventional Clinical Trials”, the ICH guideline E2A “Note for Clinical Safety Data Management” and the Safety Management Plan. CRAs will be in charge to inform investigator of each site. Acknowledgment of Receipt will be completed and signed by the investigator and then retrieved by the CRA.

In addition to this expedite reporting to Competent Authorities and Ethics committees, the overall SAE/SUSAR notified by investigator will be reported to Competent Authorities and Ethics Committees via the Annual report of Safety (see section 9.1.12.7).

If a SUSAR or IMP are likely to endanger the immediate safety of the study participant, the sponsor and the investigator should put in place urgent safety measures to protect the participants.

If urgent safety measures are put in place, Competent Authorities and Ethics Committees should be immediately informed and a protocol amendment should be submitted to the CA/EC within 15 days.

Participant will be informed about the new safety measures by the investigators as soon as possible (e.g. prior next dosing as appropriate) and through an updated informed consent.

9.1.12.4. Follow-up of AEs

Subjects who have had an AE during the treatment period must be followed clinically until all parameters (including laboratory) have either returned to normal or have stabilized or are otherwise explained.

Any newly emergent SAE after treatment is discontinued or the subject has completed the study and is considered to be related to the study drug or study participation should be recorded and reported immediately. The post-study period for the purpose of SAE reporting is up to 30 days following last visit of the study or until the SAE is resolved or stabilized.

9.1.12.5. Reporting of SUSARs

Reports of SUSARs will be reported in an expedited manner to the EC and CAs as required per French and Belgium regulations within the required time frame.

9.1.12.6. In Case of Pregnancy

If a study subject becomes or is found to be pregnant during the subject’s treatment, the Investigator must submit this information to the Sponsor. The information submitted should include the anticipated date of delivery.

Follow-up is conducted to obtain general information on the pregnancy and its outcome. The Investigator will follow the pregnancy until completion (or until pregnancy termination) and notify the Sponsor of the outcome.

If the outcome of the pregnancy meets the criteria for an SAE (i.e. ectopic pregnancy, spontaneous abortion, intrauterine fetal demise, neonatal death, or congenital anomaly, the Investigator should follow the procedures for reporting SAEs.

Male subjects whose female partner has become pregnant during the study will be requested to report to the Principal investigator on the follow-up and outcome of the pregnancy, if his partner consents to provide this information.

9.1.12.7. Development Safety Update Reports

A DSUR will be submitted once a year throughout the clinical trial to the national CA and the EC according to applicable regulations and requirements.

10. QUALITY CONTROL AND QUALITY ASSURANCE

The study will be conducted according to GCP as outlined by ICH Topic E6 step 5 guidelines. The Sponsor maintains a quality assurance system with written SOPs to ensure that clinical trials are conducted and data are generated, documented and reported in compliance with the protocol, GCP and applicable regulatory requirements.

10.1. Audits and Inspections

The study may be audited according to the Sponsor and vaccine developer's QA inspection programs. The purpose of the audit is to determine whether or not the study is being conducted and monitored in compliance with study protocol and ICH GCP guideline. Audit visit(s) will be arranged in advance with site personnel at a mutually acceptable time.

The Investigator should understand that source documents for this trial should be made available to appropriately qualified personnel from the Sponsor quality assurance or its designees or to regulatory authority inspectors after appropriate notification. The verification of the CRF data must be by direct inspection of source documents. These audits or inspections may take place at any time, during or after the study, and are based on the national regulations, as well as ICH guidelines.

Please note that IMP handling may be potentially audited by the vaccine developer.

Furthermore, CEPI, as funder of the start-up activities, reserves the right to perform, pre-, during or post-study audits by professionally trained auditors.

10.2. Study Monitoring

Monitoring of the study is the responsibility of the Sponsor and may be delegated to a CRO. Study monitors (one in charge of data audit and one in charge of IMPs accountability) will advise the Investigator and the pharmacist regarding the practical conduct of the study and maintaining compliance with the protocol, GCP and all applicable regulatory requirements.

Before study initiation, at a site initiation visit or at an Investigator's meeting, a CRO representative will review the protocol and CRFs with the Investigator and his staff.

Throughout the course of the study, the study monitor in charge of data audit will remain blinded. He/She will oversee the conduct and the progress of the study by frequent contacts with the Investigator. This will include telephone calls and on-site visits. During the on-site visits, the eCRF will be reviewed for completeness with corresponding source documents and may periodically request review of the Investigator study file to ensure completeness of documentation in all respects of clinical study conduct. As

part of the data audit, source documents will be made available for review by the study monitor. the unblinded study monitor will perform IMPs accountability checks at pharmacy.

Periodically, some or all of the facilities used in the study (e.g., local laboratory, pharmacy) may be reviewed. Monitoring visits will be arranged in advance with site personnel at a mutually acceptable time. Sufficient time must be allowed by the site personnel for the monitor to review CRFs and relevant source documents. The Investigator should be available to answer questions or resolve data clarifications. The Investigator or appointed delegate will receive the study monitor during these on-site visits, cooperate in providing the documents for inspection, and respond to inquiries.

The Investigator will ensure that the study participants are aware of and consent that personal information may be scrutinized during the data verification process as part of study-related monitoring and auditing by properly authorized persons associated with The Sponsor or inspection by domestic and/or foreign regulatory authorities. However, participation and personal information should be treated as strictly confidential to the extent that the applicable law permits and not be publicly available.

Upon completion of the study, the study monitor will arrange for a final review of the study files after which the files should be secured for the appropriate time period.

10.3. Quality Laboratory Standards

Laboratory tests or evaluations described in this protocol will be conducted in accordance with quality laboratory standards as described in the SOPs of the local institution laboratory and central laboratories.

Before the study begins, the laboratories to be used in the study will provide a list of the reference ranges for all laboratory tests to be undertaken and details of the method used for quality control. These will be held in the Investigator file and the trial master file. The methods employed for each assay should be available on request. Any change in the laboratory, its procedures, references, values, etc. during the study must be notified promptly to the Sponsor.

10.4. Study Documentation

Study documents will include the following:

- Signed ICFs
- Source documents (e.g., subject files, medical notes, study worksheets)
- Investigator copies of the CRFs and SAE reports
- Investigator site file + contents
- Laboratory manual
- Pharmacy manual

Upon completion of the study, the study monitor will arrange for a final review of the study files after which the files should be secured for the appropriate time period.

10.5. Source Document

The Investigator will permit study-related monitoring, audits by or on behalf of the Sponsor, regulatory inspections providing direct access to source data documents. Source documents are original records in

which raw data are first recorded. These may be office/clinic/hospital records, charts, diaries, ultrasound images, and laboratory results, ECG printouts, pharmacy records, care records, completed scales for each study participant and/or worksheets provided by the Sponsor. Source documents should be kept in a secure and limited access area. All source documents must be accurate, clear, unambiguous, permanent and capable of being audited. They should be made using a permanent form of recording (ink, typing, printing, optical disc, etc.). They should not be obscured by correcting fluid or have temporary attachments (such as removable self-stick notes). Source documents that are computer generated and stored electronically.

Source data for subjects registered to the study should indicate date ICF was signed, participation in clinical protocol number and title, treatment number, evidence that inclusion/exclusion criteria have been met.

10.6. Recording of Data on Case Report Form (CRF)

No data will be directly entered into the CRF without source documentation.

Completed, reviewed and signed CRFs must be available for monitoring and collection by the monitor at the end of the study.

All corrections on a CRF and on source data/documents must be made in a way which does not obscure the original entry. The correct data must be inserted, dated and initialled by relevant, authorized study site personnel. For eSource Data any changes or correction should be available via the audit trail. If the reason for the correction is not obvious, an explanation should be provided.

10.7. Investigator Site File

All documents required for the conduct of the study as specified in the ICH-GCP guidelines will be maintained by the Investigator in an orderly manner and made available for monitoring and/or auditing by the Sponsor, the vaccine developer and regulatory agencies.

10.8. Retention of Study Data

It is the responsibility of the Principal Investigator to maintain a comprehensive and centralized filing system of all relevant documentation. Investigators will be instructed to retain all study records required by the Sponsor as well as the regulatory documents in a secure and safe facility with limited access for at least 25 years after the completion of the study. Further retention, if required, will be negotiated at the end of this 25-year period. In that case the Sponsor will notify, in writing, the Principal Investigator when the clinical study data may be discarded. The Principal Investigator will take measures to prevent accidental or premature destruction of these documents.

11. DATA COLLECTION AND MANAGEMENT

11.1. Data collection

During each study visit, the investigator will collect and maintain notes in the participant's study records to document all procedures, significant observations and assessments, which are regarded as source data. Additionally, diaries and laboratory result reports signed and dated by the investigator, have to be kept within the participant's records. Changes to information in the study record and other source documents will

be initiated and dated on the day the change is made or available via audit trail in case of eSource data. All documents will be stored safely under confidential conditions

11.2. Data Management

An electronic CRF (eCRF) will be filled-in by the Investigator and/or his/her designee.

Front-end edit checks will run at the time of data collection and back-end edit checks will be used by the Data Manager to check for discrepancies and to ensure consistency and completeness of the data.

Safety assessments will be processed locally and the results will be entered in the eCRF by the Investigator and/or his/her designee.

Medical history, adverse events and concomitant procedures will be coded using the Medical Dictionary for Regulatory Activities (MedDRA) dictionary; medications will be coded using the WHO Drug Dictionary and Anatomical Therapeutic Chemical classification (ATC).

Access to electronic systems used for data collection will be granted to the study personnel only after appropriate training.

Once the database has been declared to be complete and accurate, it will be locked, the randomization codes will be opened and the planned statistical analysis will be performed.

If the database is unlocked after the initial lock, the process must be carefully controlled and documented; updates to the study data must be authorized by sponsor.

12. DATA ANALYSIS AND STATISTICAL PROCEDURES

This section outlines the data analysis strategy and statistical procedures to be employed when addressing the primary, secondary and exploratory endpoints of the study. A Statistical Analysis Plan will be further prepared to complement this section of the protocol.

Intermediate reports including safety and immunogenicity data will be provided:

1. Intermediate Report 1 (IR1): After all six sentinel subjects completed visit 4 (day 28)
2. Intermediate Report 2 (IR2): After all six sentinel subjects completed visit 5 (day 42)
3. Intermediate Report 3 (IR3): After all (or at least 50% depending on the enrolment rate) subjects completed visit 4 (day 28).
4. Interim analysis for interim CSR after all subjects completed visit 7 (day 91) or the Early Termination visit (ET)

The purpose of these intermediate analyses is to provide safety and some immunogenicity data for further SARS-CoV-2 vaccine development. Intermediate analyses will also be presented to an independent data review monitoring board (DSMB).

An interim analysis for the preparation of an interim CSR will be generated. Upon request, the DSMB members will have access to interim CSR.

The final analysis (final CSR) will be conducted once the last participant has completed the study.

12.1. Per-protocol and intention to treat analyses

The following populations will be defined and analyzed:

- In the Modified Intention To Treat (Modified ITT) population, all randomized/assigned subjects who received at least one injection are included in the analysis in the group in which they were initially randomized.
- The Per Protocol (PP) population is defined as all randomized/assigned subjects who received two injections according to protocol and completed the study without major protocol deviations. The PP analysis will be conducted based on the group in which the subjects were initially randomized/assigned.
- The modified ITT population will be used for the safety analyses, and will include sentinel subjects. The immunogenicity analyses will be performed in participants having received at least one injection (modified ITT population) as well as in participants having received two injections (PP population). For immunogenicity analyses, sentinel subjects will be included.

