| 
21. Statistical analysis
 | 
The Statistical Analysis Plan will be issued before any trial data are made available. The plan will determine all necessary data preparation steps (e.g. additional validations, generation of new variables), definitions (e.g. analysis sets) and statistical analyses (e.g. models, outputs such as tables and graphs).
 
All participants entered into the study who receive at least one vaccination will be included in the safety analysis. For solicited local, solicited systemic and unsolicited AEs, the number and percentage of participants with AEs will be summarized for each cohorts, overall, by system organ class /preferred term, AE grade, and relatedness. Solicited (local and systemic) and unsolicited AEs will be analyzed descriptively. The secondary and exploratory immunogenicity endpoints will be analyzed within each group, using appropriate tests.
 |
| 
22. Interim Analysis
 | 
Intermediate reports (no database lock) and interim analysis (with database lock) including safety and some immunogenicity data will be performed:
 
 1. Intermediate Report 1: After all six sentinel subjects completed visit 4 (day 28) 2. Intermediate Report 2: After all six sentinel subjects completed visit 5 (day 42) 3. Intermediate Report 3: After all (or at least 50% depending on the enrolment rate) subjects completed visit 4 (day 28) 4. Interim analysis for interim CSR after all subjects completed visit 7 (day 91) or the Early Termination visit (ET) 
The purpose of these intermediate analyses is to provide safety and some immunogenicity data for further SARS-CoV-2 vaccine development in outbreak situation. Intermediate analyses will also be presented to an independent data review monitoring board (DSMB). DSMB recommendations regarding further study conduct and/or protocol modifications will be considered by the sponsor. An interim analysis for the preparation of an interim CSR will be generated. Upon request, the DSMB members will have access to this interim CSR. The final analysis (final CSR) will be conducted once the last participant has completed the study.
 |

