2.2. Outcomes

2.2.1. Primary outcome measures

- Rate of solicited Adverse Event up to 14 days after each injection.
- Rate of unsolicited AE up to 28 days after each injection.
- Rate of serious adverse events (SAEs) serious adverse reactions (SARs), suspected unexpected serious adverse reactions (SUSARs) and adverse events of special interest (AESI) all along the study period.

Safety and tolerability will be assessed after each vaccination and participants will remain under observation at the study site for at least one hour for presence of any acute reactions and solicited events and by means of a diary completed by the participants for 14 days after each vaccination (from day 0 up to day 14 and from day 28 up to day 42). For each AE/SAE/AESI, the intensity and the relationship to vaccination will be reported and will be evaluated by the investigator.

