4.8. Individual participants halting rules

The following are specific criteria for discontinuing individual participants from further vaccination, but not from completing scheduled follow-up assessments, unless the participant is explicitly withdrawn from the study:

- Participants who experienced a Serious Adverse Reaction (i.e. a Serious Adverse Event considered at least possibly related to vaccine).
- Participants who experienced a severe (grade 3 or higher) non-serious adverse event considered as at least possibly related to the vaccine
- Participants who develop a medical condition for which continued participation, in the opinion of the investigator, would pose a risk to the participant or would be likely to confound interpretation of the results
- Participants with a confirmed SARS CoV-2 infection given by a positive RT-PCR or a positive serology.
- Participants who donate whole blood or blood derivatives, tissue or organ all along the study.
- Participants who become pregnant during the treatment phase of the study.
- Participants not using a reliable method of contraception
- Participants who experience hypersensitivity reaction such as anaphylaxis within 24 hours or generalized urticaria within 72 hours after administration of the study vaccine
- Participants who use immunosuppressive drugs
- Participants who receive immunoglobulin or other blood product before study completion.
- Participants who live and/or work with severely immunocompromised people, pregnant women, lactating women, children under 12 months old, or any other individual that, in the judgment of the investigator, might be at increased risk from the first vaccination (D0) up to 28 days after the second vaccination (D56).

If any of these occur, appropriate measures to treat the participant will be taken and the participant will be asked to perform an ET visit if the participant is withdrawn (for any reason) from the study. The sponsor will be notified immediately.

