12.3. Analysis of Safety objectives

All treated subjects will be included in the safety analysis. All adverse events will be coded according to coding dictionaries (MedDRA version 23.0 or higher) for System Organ Class (SOC) and Preferred Term (PT).

The adverse events will then be grouped by MedDRA preferred term into frequency tables according to SOC. These summaries will be presented by vaccination group and by interval of study observation. The overall frequencies per vaccine group as well as frequencies according to severity will be calculated for solicited (local and general) AEs, unsolicited AEs, serious AEs (SAEs), adverse events of special interest (AESI) and clinically significant abnormal laboratory values (grade 3 or 4). Solicited (local and systemic) and unsolicited AEs will be compared between treatment groups using Fisher-Freeman-Halton tests.

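### Safety is grouped as randomised with open-label sentinels in the between-group adverse event tests, and the synopsis and section 12.3 disagree on whether those tests are done

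*Protocol*

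**What the plan says.** Section 12.1 of the protocol defines a modified ITT population of randomised or assigned subjects with at least one injection, who "are included in the analysis in the group in which they were initially randomized". It then gives that population its role: "The modified ITT population will be used for the safety analyses, and will include sentinel subjects".

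Section 12.3 adds "All treated subjects will be included in the safety analysis" and, on layout, "These summaries will be presented by vaccination group and by interval of study observation". These sentences settle who is counted and how the tables are cut. They do not say that AEs are assigned to the product received. Section 12.3 also states that "Solicited (local and systemic) and unsolicited AEs will be compared between treatment groups using Fisher-Freeman-Halton tests".

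Item 21 of the synopsis says of the same events: "Solicited (local and systemic) and unsolicited AEs will be analyzed descriptively". The French synopsis says the same.

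The primary outcomes in 2.2.1 are defined per injection, for example "Rate of solicited Adverse Event up to 14 days after each injection". Section 4.8 lists "specific criteria for discontinuing individual participants from further vaccination" while keeping those participants in follow-up.

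Sections 3.2, 3.3 and 4.11 describe the sentinels: six open-label, non-randomised vaccinees enrolled first, at one site, three in cohort A and three in cohort B. Sections 7.1 and 7.2 give only them a 24-hour call after each injection and a Day 7 visit with injection-site examination and safety laboratory tests.

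**The concern.** Safety and tolerability are the primary objective, so the safety set decides what the trial's main tables mean. Three things in the current wording work against a clean reading.

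First, grouping as randomised is the usual choice for questions about assignment. For harms, the question is what happened to people given a particular preparation. The trial handles low dose, high dose and saline, and cohort C changes from vaccine to saline at the second injection. If anyone is given the wrong one, 12.1 as written files their events under a product they did not receive.

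Second, a between-group test relies on comparable ascertainment and on random allocation. The sentinels know what they received, were not randomised, and are contacted and examined more often. They sit in two of the groups only.

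Third, two current statements on the primary endpoint cannot both govern: one promises description, the other hypothesis tests. The choice should not be left open until data are in hand.

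**Working it through.** **Inputs from the protocol.** Table 1 in 3.3 (sentinel, main group, placebo): A 3, 21, 6; B 3, 21, 6; C 0, 24, 6. Section 4.11.1: 84 randomised, 7:2 in A and B, 4:1 in C. Section 12.6: no formal sample size calculation. The protocol gives no AE rates, no dosing-error rate and no rate of missed second injections, so these are assumed below and shown as ranges.

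**The plan's own counts reproduce.** 30 + 30 + 30 = 90; 27 + 27 + 30 = 84; 21:6 = 7:2; 24:6 = 4:1. Vaccinees are 24 per cohort. Placebo is 6 + 6 + 6 = 18 if pooled. Section 12.4 pools placebo for immunogenicity; I assume the same for safety.

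**1. Grouping as randomised.** With m placebo participants wrongly given vaccine, the apparent placebo rate is [(18 − m)·p_P + m·p_V]/18, an expected shift of m(p_V − p_P)/18. With m vaccinees wrongly given saline, the cohort rate falls by m(p_V − p_P)/24.

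| Assumed vaccine / placebo AE rate | Placebo shift, m = 1 | Vaccine cohort shift, m = 1 |
|---|---|---|
| 30% / 10% | 0.20/18 = +1.1 points | 0.20/24 = −0.8 points |
| 60% / 20% | 0.40/18 = +2.2 points | 0.40/24 = −1.7 points |
| 80% / 40% | 0.40/18 = +2.2 points | 0.40/24 = −1.7 points |

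The largest possible effect of one such error on pooled placebo is one extra event in 18: 1/18 = 5.6 points. With m = 0 the shift is zero.

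**2. Sentinels.** Their share of vaccinees is 3/24 = 12.5% in A and in B, 0/24 in C and 0/18 in placebo. If they report AEs e points more often than blinded vaccinees, the cohort rate rises by 0.125·e. For e = 10, 20, 30 and 40 points (assumed) the rise is 1.25, 2.5, 3.75 and 5 points. The direction is upward, in A and B only.

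**3. Injection-2 denominator.** This shows what follows if non-recipients were counted; the protocol does not say that they are. With k of 24 not receiving injection 2, a true rate p among recipients would appear as p(24 − k)/24, a relative understatement of k/24: 4.2%, 8.3%, 12.5% and 16.7% for k = 1 to 4. At p = 60% the table would show 57.5%, 55.0%, 52.5% and 50.0%. The loss over k = 1 to 4 is 1.3 to 5 points at p = 30% and 3.3 to 13.3 points at p = 80%.

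**4. Scale.** The exact 95% interval for 14/24 (58.3%) runs from 36.6% to 77.9%, about 41 points.

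**5. Synopsis against 12.3.** Both sentences concern solicited (local and systemic) and unsolicited AEs. Neither is marked as superseded, and neither refers to the other.

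**The case against.** The best defence is that most of this may never matter. Misattribution needs a dosing error. Sections 4.11.2, 5.4.3 and 5.4.5 put preparation in the hands of unblinded pharmacy staff working from the allocation list, with accountability checked per participant. That stands: with no error nothing changes, and the direction of any error varies. A low-dose participant given high dose would raise the apparent rate in A, for instance. Saline at Day 28 in cohort C is the assigned regimen and is not in itself an attribution problem.

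A reader might infer more: that the primary AE rates as planned are misattributed and diluted, and that people barred from injection 2 are counted in the post-injection-2 denominator. The document does not support this. Section 12.1 defines membership of a population, not the number at risk in each interval. Section 12.3 summarises by interval, which fits a denominator of recipients, and a statistical analysis plan may set it so. Section 4.8 also stops injection 2 for reasons other than reactions, such as infection, pregnancy or blood donation. Stating the denominator is therefore a useful clarification, since related severe or serious events are among the reasons for stopping, but its absence is not an error.

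Nor do the sentinels dilute or misattribute anything. They receive their cohort's assigned vaccine, and any bias would more likely raise A and B. Their inclusion is openly stated and sensible in the descriptive tables of a first-in-human trial. The same 14-day diary (8.2) collects solicited AEs from everyone, which limits the effect of the extra contacts. What remains is their place in a between-group test.

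Finally, the conflict between the synopsis and 12.3 could be settled in either direction. Section 12.2 already provides exact binomial intervals for proportions, so replacing the tests is one option among several.

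**Conclusion.** The point holds in a limited form and should be corrected. The protocol prescribes grouping as randomised for safety and offers no grouping by product received. Under the assumed AE rates, one dosing error shifts a rate by about 1 to 2 points, at most 5.6 points in pooled placebo; with no errors the effect is nil. Six open-label, non-randomised sentinels enter the between-group AE tests on one side only. The possible inflation in A and B is about 1 to 5 points if they report 10 to 40 points more often, an assumption for which the protocol gives no basis. The synopsis and 12.3 contradict each other on the method for the primary endpoint.

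None of these effects is large against an interval some 41 points wide at 24 per group. The case for acting is that the wording concerns the primary objective, is wrong or contradictory as it stands, and is cheap to correct before data are seen.

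**What to change.** - In 12.1, define a separate safety population: everyone with at least one injection, analysed by the product actually received. Keep the modified ITT definition for immunogenicity.
- In 12.3, state that rates after each injection use the recipients of that injection as denominator. This is a clarification.
- Keep the sentinels in the descriptive safety tables, identifiable as such, but base any between-group AE comparison on the 84 randomised participants (21 in A, 21 in B, 24 in C, 18 placebo).
- Reconcile item 21 of the synopsis (both languages) with 12.3. One way is to report vaccine-minus-pooled-placebo differences with exact 95% confidence intervals as descriptive results. If the tests are kept, the synopsis should say so.

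The cost is a few sentences in 12.1, 12.3 and the synopsis. No visit, procedure or sample size changes. The one statistical price is that comparisons involving A and B rest on 21 rather than 24 vaccinees each.
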